9.3 Arm 2 Cycles 5+

	Cycle (1 cycle = 28 days) ^R												Follow-up prior to progression	Follow-up after progression
	5				6				7+					
	Week ^K													
	13	14	15	16	17	18	19	20	21	22	23	24		
PHYSICAL														
History and physical exam	X				X				X				X ^N	X ^Q
Weight and performance status	X				X				X				X ^N	X ^Q
Toxicity notation	X				X				X				X ^P	X ^P
Disease assessments												X ^M	X ^M	
LABORATORY														
ANC, platelets, and hemoglobin	X				X				X				X ^P	X ^P
AST, ALT, and total bilirubin	X				X				X				X ^P	X ^P
Serum creatinine	X				X				X				X ^P	X ^P
Creatinine phosphokinase (CPK), Troponin, and Cardiology consultation ^B														
TSH, Free T4, Free T3 ^C	X				X				X					
X-RAYS AND SCANS														
MRI or CT for disease assessment ^S												X ^M	X ^M	
Electrocardiogram (ECG) and Echocardiogram (Echo) ^D														
TREATMENT														
Nivolumab 480 mg	X				X				X					

Click here for [footnotes](#).

Note: Forms are found on the protocol abstract page of the SWOG website (www.swog.org). The schedule for submission of these forms is listed in [Section 14.0](#).

Note: Unless indicated otherwise in the protocol, scheduled procedures and assessments (treatment administration, toxicity assessment, disease assessment, specimen collection and follow-up activities) must follow the established SWOG guidelines as outlined in <http://swog.org/Visitors/QA/Documents/Best%20Practices%20update.pdf>.

Footnotes

- B Only for patients with symptoms of congestive heart failure (CHF), cardiomyopathy, myocarditis, myocardial infarction, or exposure to cardiotoxic medications. Required pre-registration (see [Section 5.3n](#)). After that, perform as clinically indicated.
- C Free T3 and Free T4 are only required if TSH results are abnormal.
- D Only for patients with a known history of congestive heart failure (CHF), cardiomyopathy, myocarditis, myocardial infarction, exposure to cardiotoxic medications, or with a clinical history suggestive of any of these conditions. Required pre-registration (see [Section 5.3m](#)). After that, perform as clinically indicated.
- K Weeks measured from start of treatment, provided that the patient does not have any treatment delays
- M Performed every 12 weeks (i.e., at *completion* of Week 24, 36, etc.) for 3 years from time of registration or until progression.
- N Every 12 weeks until progression
- P Every 4 weeks until resolution of adverse events
- Q At least every 6 months (+/- 2 weeks) until 2 years after registration, then annually (+/- 4 weeks) until 3 years after registration.
- R Protocol treatment and parameters will continue on this same schedule until one of the criteria in [Section 7.5](#) is met.
- S CT or MRI of the chest, abdomen, and pelvis should be performed at baseline and all subsequent assessments. Additionally, for patients with known assessable scalp or neck disease, a CT or of the head/face/neck should be performed at baseline and all subsequent assessments. Patients with known assessable extremity disease should have the affected extremity also measured by CT or MRI at baseline and all subsequent visits. Patients with a history of central nervous system metastases must have MRI of the brain at baseline and at all subsequent assessments.

10.0 CRITERIA FOR EVALUATION AND ENDPOINT ANALYSIS

10.1 Measurability of Lesions

a. **Measurable disease:** Measurable disease is defined differently for lymph nodes compared with other disease and will be addressed in a separate section below.

1. Lesions that can be accurately measured in at least one dimension (longest diameter to be recorded) as ≥ 2.0 cm by chest x-ray, by ≥ 1.0 cm with CT or MRI scans (see below for additional considerations for size based on the imaging approach), or ≥ 1.0 cm with calipers by clinical exam. All tumor measurements must be recorded in decimal fractions of centimeters (or millimeters).

The defined measurability of lesions on CT scan is based on the assumption that CT slice thickness is 0.5 cm or less. If CT scans have slice thickness greater than 0.5 cm, the minimum size for a measurable lesion should be twice the slice thickness.

2. **Malignant lymph nodes** are to be considered pathologically enlarged and measurable if it measures ≥ 1.5 cm in **SHORT AXIS** (greatest diameter perpendicular to the long axis of the lymph node) when assessed by scan (CT scan slice recommended being no greater than 0.5 cm).

b. **Non-measurable disease:** All other lesions (or sites of disease), including small lesions (longest diameter < 1.0 cm or pathologic lymph nodes with ≥ 1.0 cm to < 1.5 cm short axis), are considered non-measurable disease. Bone lesions, leptomeningeal disease, ascites, pleural/pericardial effusions, lymphangitis cutis/pulmonitis, inflammatory breast disease, and abdominal masses (not followed by CT or MRI), are considered non-measurable as are previously radiated lesions that have not progressed.

c. **Notes on measurability**

1. For CT and MRIs, the same type of scanner should be used and the image acquisition protocol should be followed as closely as possible to prior scans. Body scans should be performed with breath-hold scanning techniques, if possible.
2. PET-CT: At present, the low dose or attenuation correction CT portion of a PET-CT is not always of optimal diagnostic CT quality for use with RECIST measurements. However, if the site can document that the CT performed as part of a PET-CT is of identical diagnostic quality to a diagnostic CT, then the CT portion of the PET-CT can be used for RECIST measurements and can be used interchangeably with conventional CT.
3. Ultrasound: Ultrasound is not useful in assessment of lesion size and should not be used as a method of measurement.
4. Cystic lesions that meet the criteria for radiographically defined simple cysts should not be considered as malignant lesions (neither measurable nor non-measurable) since they are, by definition simple cysts.
5. If a target lesion becomes very small some radiologists indicate that it is too small to measure. If the lesion is actually still present, a default

measurement of 0.5 cm should be applied. If the radiologist believes the lesion has gone, a default measurement of 0.0cm should be recorded.

10.2 Objective Status at Each Disease Evaluation

Objective Status is to be recorded at each evaluation. All measurable lesions up to a maximum of 2 lesions per organ 5 lesions in total, representative of all involved organs, should be identified as *target* lesions at baseline. All other lesions (or sites of disease) including any measurable lesions over and above the 5 target lesions should be identified as *non-target* lesions. Measurements must be provided for target measurable lesions, while presence or absence must be noted for non-target measurable and non-measurable disease.

For studies that use disease progression as an endpoint, whole body scanning at specific intervals is necessary to determine that progression is NOT present outside of the “target” areas. Therefore, in these studies it is not acceptable to image only the “target” areas of the body in follow-up scans. For study-specific imaging requirements, see the Study Calendar in [Section 9.0](#).

- a. **Complete Response (CR):** Complete disappearance of all target and non-target lesions (with the exception of lymph nodes mentioned below). No new lesions. No disease related symptoms. Any lymph nodes (whether target or non-target) must have reduction in short axis to < 1.0 cm. All disease must be assessed using the same technique as baseline.
- b. **Partial Response (PR):** Applies only to patients with at least one measurable lesion. Greater than or equal to 30% decrease under baseline of the sum of appropriate diameters of all target measurable lesions. No unequivocal progression of non-measurable disease. No new lesions. All target measurable lesions must be assessed using the same techniques as baseline.
- c. **Stable:** Does not qualify for CR, PR, Progression or Symptomatic Deterioration. All target measurable lesions must be assessed using the same techniques as baseline.
- d. **Progression:** One or more of the following must occur: 20% increase in the sum of appropriate diameters of target measurable lesions over smallest sum observed (over baseline if no decrease during therapy) using the same techniques as baseline, as well as an absolute increase of at least 0.5 cm. Unequivocal progression of non-measurable disease in the opinion of the treating physician (an explanation must be provided). Appearance of any new lesion/site. Death due to disease without prior documentation of progression and without symptomatic deterioration (see [Section 10.2e](#)).

Notes regarding new lesions: FDG-PET imaging can complement regular scans in identifying new lesions according to the following algorithm.

1. Negative FDG-PET at baseline, with a positive FDG-PET at follow-up is a sign of progression based on a new lesion.
2. No FDG-PET at baseline and a positive FDG-PET at follow-up corresponding to a potential new site of disease must have a confirmation by anatomical assessment (e.g., CT, MRI, x-ray) as new site of disease to be considered progressive disease. In such a case, the date of progressive disease will be the date of the initial abnormal FDG-PET.

- e. **Symptomatic deterioration:** Global deterioration of health status requiring discontinuation of treatment without objective evidence of progression. Efforts should be made to obtain objective evidence of progression after discontinuation.
- f. **Assessment inadequate, objective status unknown.** Progression or symptomatic deterioration has not been documented, and one or more target measurable lesions have not been assessed or inconsistent assessment methods were used.
- g. **Objective status notes:**
1. Non-measurable and non-target measurable disease do not affect Objective Status in determination of CR (must be absent--a patient who otherwise has a CR, but who has non-measurable or non-target measurable disease present or not assessed, will be classified as having a PR). However, non-measurable and non-target lesions are included in determination of progression (if new sites of disease develop or if unequivocal progression occurs in the opinion of the treating physician).
 2. An objective status of PR or stable cannot follow one of CR. Stable can follow PR only in the rare case that tumor increases too little to qualify as progression, but enough that a previously documented 30% decrease no longer holds.
 3. In cases for which initial flare reaction is possible (hypercalcemia, increased bone pain, erythema of skin lesions), objective status is not progression unless either symptoms persist beyond 4 weeks or there is additional evidence of progression.
 4. Lesions that appear to increase in size due to presence of necrotic tissue will not be considered to have progressed.
 5. For bone disease documented on bone scan only, increased uptake does not constitute unequivocal progression. However, increase in the soft tissue component of a lesion as measured by CT or MRI would constitute progression.
 6. Appearance of new pleural effusions does not constitute unequivocal progression unless cytologically proven of neoplastic origin, since some effusions are a toxicity related to therapy or other medical conditions. Increase in the size of an existing effusion does not constitute unequivocal progression, since the fluid status of the patient could alter the size of the effusion.
 7. If CR determination depends on a lesion for which the status is unclear by the required tests, it is recommended the residual lesion be investigated with biopsy or fine needle aspirate.

10.3 Best Response

This is calculated from the sequence of objective statuses.

- a. CR: Two or more objective statuses of CR a minimum of four weeks apart documented before progression or symptomatic deterioration.

- b. PR: Two or more objective statuses of PR or better a minimum of four weeks apart documented before progression or symptomatic deterioration, but not qualifying as CR.
- c. Unconfirmed CR: One objective status of CR documented before progression or symptomatic deterioration but not qualifying as CR or PR.
- d. Unconfirmed PR: One objective status of PR documented before progression or symptomatic deterioration but not qualifying as CR, PR or unconfirmed CR.
- e. Stable/no response: At least one objective status of stable/no response documented at least 6 weeks after registration and before progression or symptomatic deterioration, but not qualifying as anything else above.
- f. Increasing disease: Objective status of progression within 12 weeks of registration, not qualifying as anything else above.
- g. Symptomatic deterioration: Objective status of symptomatic deterioration within 12 weeks of registration, not qualifying as anything else above.

Inadequate assessment, response unknown: Progression or symptomatic deterioration greater than 12 weeks after registration and no other response category applies.

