 - Hospitalization for \leq Grade 2 adverse events where the primary reason for hospitalization is to expedite the clinical work-up.
 - Patients with the following conditions where in the treating investigator's opinion continuing study drug administration is justified based on the potential for continued clinical benefit:
 - Patients treated with systemic steroids for less than 2 weeks without evidence of autoimmune disease requiring steroids treatment
 - Grade 2 skin rash treated with topical steroids for less than 4 weeks
 - Grade 2 ocular toxicity that has completely responded to topical therapy within 4 weeks
 - Endocrinopathies where clinical symptoms are controlled with appropriate hormone replacement therapy. **Note:** Ipilimumab may not be restarted while the patient is being treated with systemic corticosteroids except for patients on stable doses of hormone replacement therapy such as hydrocortisone.
- e. Allowance for ipilimumab dose delay
- In general, patients who meet criteria to resume ipilimumab will also have met criteria to resume nivolumab with ipilimumab, so it should be feasible to synchronize dosing of both drugs when resuming ipilimumab. In order to facilitate this, the dosing calendar days of nivolumab and ipilimumab may be adjusted within a +/- 5 day window, as long as consecutive nivolumab doses are given at least 12 calendar days apart.
 - If an ipilimumab dose is delayed beyond 6 weeks from the prior ipilimumab dose, then subsequent nivolumab doses should be rescheduled to maintain at least a 3-week interval between consecutive ipilimumab doses.

- Dosing delays to manage drug-related adverse events, such as prolonged steroid tapers, are allowed. Disease assessments should continue as per protocol even if dosing is delayed.
- Dosing delays resulting in no ipilimumab dosing for > 6 weeks that occur for non-drug-related reasons may be allowed if approved by the Study Chairs. Disease assessments should continue as per protocol even if dosing is delayed.
- In event of any Grade 2 adverse event experienced while on combination nivolumab plus ipilimumab therapy, patient may resume treatment/may be continued on nivolumab monotherapy alone, at the discretion of the treating investigator
- Ipilimumab will not be given as monotherapy for Arm 2.

NOTE: If adverse events result in permanent discontinuation of ipilimumab, then subsequently manage dose delays under Management/Next Dose for nivolumab alone

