- A To be performed on or prior to Day 1 and on Day 21-35 (Day 28 +/- 7 days). The first biopsy should be performed within 28 days prior to Day 1. If it is not feasible to obtain this biopsy, tissue that was collected at any time since demonstrated progression on PD-1 or PD-L1 therapy may be substituted provided that 30 unstained slides are available.
- B Only for patients with symptoms of congestive heart failure (CHF), cardiomyopathy, myocarditis, myocardial infarction, or exposure to cardiotoxic medications. Required pre-registration (see [Section 5.3n](#)). After that, perform as clinically indicated.
- C Free T3 and Free T4 are only required if TSH results are abnormal.
- D Only for patients with a known history of congestive heart failure (CHF), cardiomyopathy, myocarditis, myocardial infarction, exposure to cardiotoxic medications, or with a clinical history suggestive of any of these conditions. Required pre-registration (see [Section 5.3m](#)). After that, perform as clinically indicated.
- E Collected prior to previous anti-PD-1 or anti-PD-L1 treatment
- F To be drawn on or prior to Day 1 (after registration and within 28 days) and on Day 21-35 (Day 28 +/- 7 days). If feasible, Day 1 blood should be drawn on the same day as the baseline tissue biopsy. Day 28 Blood must be drawn on same day as the Day 28 tissue biopsy.
- G Required time frame is detailed in [Section 5.0](#).
- H Only for females of reproductive potential (see [Section 5.3p](#))
- J Only required for patients with a known history of HIV (see [Section 5.3g](#))
- K Weeks measured from start of treatment, provided that the patient does not have any treatment delays
- L If pre-registration exam/lab was performed within 14 days prior to Cycle 1 Day 1, this exam/lab does not need to be repeated on Cycle 1 Day 1.
- M Performed at completion of Week 12
- N Every 12 weeks until progression
- P Every 3 weeks until resolution of adverse events
- Q At least every 6 months (+/- 2 weeks) until 2 years after registration, then annually (+/- 4 weeks) until 3 years after registration.
- R Though weight should be checked at each visit, weight-based dosing should be calculated using baseline weight unless weight has changed from last dose by more than 10%.

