13.0 REGISTRATION GUIDELINES

13.1 Registration Timing

Patients must be registered prior to initiation of treatment (no more than seven calendar days prior to planned start of treatment).

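### The 12-week cut-off in Section 10.3 runs from registration and usually closes before the first scheduled scan, so most first-scan progressors are classed as response unknown

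*Combined protocol and SAP*

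**What the plan says.** Section 10.3 derives best response from the sequence of objective statuses. Item f reads "Increasing disease: Objective status of progression within 12 weeks of registration, not qualifying as anything else above". The closing category reads "Inadequate assessment, response unknown: Progression or symptomatic deterioration greater than 12 weeks after registration and no other response category applies". The stable category, item e, requires "At least one objective status of stable/no response documented at least 6 weeks after registration and before progression or symptomatic deterioration".

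The study calendars (Sections 9.1 and 9.2) give the timing of the first on-study disease assessment in both arms as "Performed at completion of Week 12". Footnote K sets the origin: "Weeks measured from start of treatment, provided that the patient does not have any treatment delays". Neither calendar schedules a disease assessment between baseline and that point. Section 13.1 allows registration "no more than seven calendar days prior to planned start of treatment".

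Section 10.2f also defines an inadequate assessment, as an objective status. It applies only where neither progression nor symptomatic deterioration has been documented and target lesions were missed or measured inconsistently.

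**The concern.** The cut-off and the scan are both set at 12 weeks but count from different days. The cut-off runs from registration and the scan from the start of treatment, so the scan normally falls just after the cut-off closes.

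A patient whose first scan shows progression has no earlier scheduled assessment that could have recorded a stable or responding status. Items a to e of Section 10.3 therefore do not apply, item f has expired, and the patient falls into the unknown category. Yet the assessment was done and its result is clear. Under Section 10.2d the status at that visit is progression, and under 10.2f it cannot be inadequate.

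At stake is the best-response distribution. Progressive disease would be under-counted and inadequate assessment over-counted. If the arms progress at the planned rates, the distortion could be larger on ipilimumab and could be misread as poorer follow-up in that arm.

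**Working it through.** **Inputs.** Cut-off of 12 weeks = 84 days from registration (10.3). First scan at completion of Week 12 from treatment start (9.1 and 9.2, footnotes K and M). Lag from registration to planned treatment start of 0 to 7 days (13.1). Median PFS of 3 and 6 months, exponential (11.2). Arm sizes of 21 and 63 (11.1).

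**Step 1: the plan's nearest stated figure.** Section 11.3 gives response-rate precision of 12.3% and 21.4%. The half-width is 1.96 × √(0.25/n): 12.35% for n = 63 and 21.39% for n = 21. The plan's figures reproduce, and this point does not dispute them.

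**Step 2: day of the first scan.** Days from registration = lag + 84.

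- Lags of 0 to 7 days give days 84, 85, 86, 87, 88, 89, 90 and 91. Only a lag of 0 is within 84 days, so 7 of the 8 permitted lags fall past the cut-off.
- If completion of Week 12 means treatment Day 84 (83 days after Day 1), the range is 83 to 90 and 6 of 8 lags fall past it.

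**Step 3: effect of a scan window.** The documents give no window, so these values are assumptions, with every combination of lag and scan day equally likely.

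- ±3 days: 10 of 56 combinations (18%) fall on or before day 84, so 82% fall past it.
- ±7 days: 36 of 120 combinations (30%) fall on or before day 84, so 70% fall past it.

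**Step 4: ceiling on the patients affected.** The proportion with a PFS event by day t is 1 − 0.5^(t/median), with 30.4375 days per month. Day 84 is 2.76 months and day 91 is 2.99 months.

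| Arm | By day 84 | By day 91 |
|---|---|---|
| Ipilimumab (median 3 months, n = 21) | 47.1%, 9.9 patients | 49.9%, 10.5 patients |
| Combination (median 6 months, n = 63) | 27.3%, 17.2 patients | 29.2%, 18.4 patients |
| Both arms | about 27 of 84 | about 29 of 84 |

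These are upper bounds on the number misclassified. They include disease deaths within 12 weeks, which 10.2d counts as progression. They also include symptomatic deterioration within 12 weeks, which has its own category in 10.3g, and progression found before day 84 by examination or an unscheduled scan, which 10.3f classifies correctly.

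**Step 5: which analyses use the category.**

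- PFS (10.5) uses the date of first documented progression, not best response.
- The response rate (11.3) keeps patients with undetermined response in the denominator as non-responders, so moving a patient between the two categories changes nothing.
- The CD8 comparison (11.1) sets patients with an objective response against those without one. Its planned count is 63 × 0.9 = 56.7, about 57, split as 14 + 43 = 57. Nothing is deducted for unknown response. Section 11.3 gives 56 for the same group, which differs only by rounding.

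**The case against.** The strongest reply is that no planned inference depends on this label. That stands: Step 5 bears it out for PFS, the response rate and the CD8 comparison. Section 11 does not commit to a table of best-response categories either; it promises response rates and waterfall plots. The damage appears wherever the categories defined in 10.3 are tabulated.

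A reader might go further and infer that primary progressors drop out of the CD8 comparison. Removing about 15 of them (63 × 0.9 × 27.3% = 15.5) would turn 14 versus 43 into 14 versus 28 and cut power at 0.875 SD from 80% to 74%. The documents do not support this. Section 11.1 defines the two groups as complements and deducts no unknowns, and Appendix 18.1 models dichotomous response status. No section excludes patients with unknown response.

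A second reply is that some first scans will meet the cut-off: a same-day start with a scan on day 84, or a scan done slightly early. This also stands. The calendars defer scheduling detail to group guidelines that are not part of the documents, so the exact share is unknown. Treatment delays do not rescue the rule, since Section 8.3 says "Disease assessments should continue as per protocol even if dosing is delayed".

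**Conclusion.** The timing conflict holds. By the documents' own dates, the first scheduled scan falls on about day 84 to 91 from registration against a cut-off of day 84. Most patients whose progression is first documented at that scan would be classed as response unknown despite an adequate assessment, in conflict with 10.2f.

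The percentages in Step 4 should be read only as ceilings: at most 27-29% of combination and 47-50% of ipilimumab patients. They rest on exponential PFS with the planned medians. The difference between arms holds only if the planned hazard ratio of 0.5 does.

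The consequence is limited to the best-response distribution. The primary analysis, the response rate and the CD8 responder comparison are unaffected, and no loss of power should be claimed. It is still worth correcting, because a stated endpoint rule gives the wrong category for a common outcome and the correction needs no new data.

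**What to change.** In 10.3f and the matching part of the unknown category, set the progression cut-off so that it includes the first scheduled disease assessment. It must be at least 91 days (13 weeks) from registration, plus whatever scan window the group guidelines allow. If that window is assumed to be 7 days, the cut-off is 98 days (14 weeks). State the window in the protocol.

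Reserve response unknown for patients without an adequate assessment, in line with 10.2f.

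The closing sentence of 10.3 combines progression with symptomatic deterioration. Split it so that the progression cut-off can move alone; symptomatic deterioration does not depend on a scheduled scan, so 10.3g can stay as it is.

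The cost is a wording change in 10.3 and an update to the response-derivation code. Sample size, the primary test and the stated response-rate precision of 12.3% and 21.4% stay as they are.
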